### 11.3. Criteria for Potentially Clinically Significant Values (PCSV)

Where adolescent criteria (age >12 to <18) are different than adult criteria (>18), the adolescent criteria are provided in [parentheses] in the combined column. The criteria inside the “Combined” column will be used for display in the reporting outputs. Applicable criteria will be applied to parameters collected in the study to identify treatment-emergent PCSV cases.

Parameter	Adults (≥18) a	Adolescents (≥12 to <18) a	Combined
Clinical Chemistry			
ALT/SGPT	>3 and ≤ 5 ULN and baseline ≤ 3 ULN >5 and ≤ 10 ULN and baseline ≤ 5 ULN >10 and ≤ 20 ULN and baseline ≤ 10 ULN >20 ULN and baseline ≤ 20 ULN	>3 and ≤ 5 ULN and baseline ≤ 3 ULN >5 and ≤ 10 ULN and baseline ≤ 5 ULN >10 and ≤ 20 ULN and baseline ≤ 10 ULN >20 ULN and baseline ≤ 20 ULN	>3 and ≤ 5 ULN and baseline ≤ 3 ULN >5 and ≤ 10 ULN and baseline ≤ 5 ULN >10 and ≤ 20 ULN and baseline ≤ 10 ULN >20 ULN and baseline ≤ 20 ULN
AST/SGOT	>3 and ≤ 5 ULN and baseline ≤ 3 ULN >5 and ≤ 10 ULN and baseline ≤ 5 ULN >10 and ≤ 20 ULN and baseline ≤ 10 ULN >20 ULN and baseline ≤ 20 ULN	>3 and ≤ 5 ULN and baseline ≤ 3 ULN >5 and ≤ 10 ULN and baseline ≤ 5 ULN >10 and ≤ 20 ULN and baseline ≤ 10 ULN >20 ULN and baseline ≤ 20 ULN	>3 and ≤ 5 ULN and baseline ≤ 3 ULN >5 and ≤ 10 ULN and baseline ≤ 5 ULN >10 and ≤ 20 ULN and baseline ≤ 10 ULN >20 ULN and baseline ≤ 20 ULN
Alkaline Phosphatase	>1.5 ULN and baseline ≤ 1.5 ULN	≥1.5 ULN and baseline <1.5 ULN	>1.5 [≥1.5] ULN and baseline ≤ 1.5 [<1.5] ULN
Total Bilirubin	>1.5 and ≤ 2 ULN and baseline ≤ 1.5 ULN >2 ULN and baseline ≤ 2.0 ULN	≥1.3 ULN and baseline < 1.3 ULN	>1.5 [≥1.3] and ≤ 2 ULN and baseline ≤ 1.5 [< 1.3] ULN >2 ULN and baseline ≤ 2.0 ULN
Conjugated Bilirubin b	(Direct Bilirubin >35% Total Bilirubin and Total Bilirubin >1.5 ULN) and (Direct Bilirubin ≤35% Total Bilirubin or Total Bilirubin ≤1.5 ULN) at baseline	(Direct Bilirubin >35% Total Bilirubin and Total Bilirubin ≥1.3 ULN) and (Direct Bilirubin ≤35% Total Bilirubin or Total Bilirubin <1.3 ULN) at baseline	(Direct Bilirubin >35% Total Bilirubin and Total Bilirubin >1.5 [≥1.3] ULN) and (Direct Bilirubin ≤35% Total Bilirubin or Total Bilirubin ≤1.5 [<1.3] ULN) at baseline
ALT or AST and Total Bilirubin	((ALT>3 ULN or AST>3 ULN) and TBILI>2 ULN) and baseline ((ALT ≤3 ULN and AST≤3 ULN) or TBILI ≤2 ULN)	((ALT>3 ULN or AST>3 ULN) and TBILI>2 ULN) and baseline ((ALT ≤3 ULN and AST≤3 ULN) or TBILI ≤2 ULN)	((ALT>3 ULN or AST>3 ULN) and TBILI>2 ULN) and baseline ((ALT ≤3 ULN and AST≤3 ULN) or TBILI ≤2 ULN)
CPK	>3 and ≤ 10 ULN and baseline ≤ 3ULN >10 ULN and baseline ≤ 10ULN	≥3 ULN and baseline < 3ULN	>3 [≥3] and ≤ 10 ULN and baseline ≤ 3 [<3] ULN >10 ULN and baseline ≤ 10ULN

Parameter	Adults (≥18) a	Adolescents (≥12 to <18) a	Combined
Creatinine	≥150 μmol/L (Adults) and baseline < 150 μmol/L >=30% change from baseline and <100% change from baseline ≥100% change from baseline	≥132μmol/L and baseline < 132μmol/L (or ≥1.5 mg/dL and baseline <1.5 mg/dL) >=30% change from baseline	≥150 [≥132] μmol/L and baseline < 150 [<132] μmol/L >=30% change from baseline and <100% change from baseline ≥100% change from baseline
Uric Acid Hyperuricemia Hypouricemia	>408 μmol/L and ≤408 μmol/L at baseline <120 μmol/L and ≥ 120 μmol/L at baseline	≥8.0 mg/dL and <8.0 mg/dl at baseline ( or ≥476 μmol/L and <476 μmol/L at baseline ≤2 mg/dL and >2 mg/dL at baseline (or ≤119 μmol/L and baseline > 119 μmol/L)	>408 [≥476] μmol/L and ≤408 [<476] μmol/L at baseline <120 μmol/L and ≥ 120 μmol/L at baseline
Blood Urea Nitrogen	≥17 mmol/L and <17 mmol/L at baseline	≥7.14 mmol/L and <7.14 mmol/L at baseline	≥17 [≥7.14] mmol/L and <17 [<7.14] mmol/L at baseline
Chloride Hypochloremia Hyperchloremia	<80 mmol/L and baseline ≥ 80 mmol/L >115 mmol/L and baseline ≤ 115 mmol/L	<80 mmol/L and baseline ≥ 80 mmol/L ≥115 mmol/L and baseline < 115 mmol/L	<80 mmol/L and baseline ≥ 80 mmol/L >115 mmol/L and baseline ≤ 115 mmol/L
Sodium Hyponatremia Hypernatremia	≤129 mmol/L and baseline > 129 mmol/L ≥160 mmol/L and baseline <160 mmol/L	≤129 mmol/L and baseline >129 mmol/L ≥150 mmol/L and baseline <150 mmol/L	≤129 mmol/L and baseline > 129 mmol/L ≥160 [≥150] mmol/L and baseline <160 [<150] mmol/L
Potassium Hypokalemia Hyperkalemia	<3 mmol/L and baseline ≥ 3 mmol/L ≥5.5 mmol/L and baseline <5.5 mmol/L	≤3.5 mmol/L and baseline >3.5 mmol/L ≥5.5 mmol/L and baseline <5.5 mmol/L	<3 [≤3.5] mmol/L and baseline ≥ 3 [>3.5] mmol/L ≥5.5 mmol/L and baseline <5.5 mmol/L
Total Cholesterol	≥7.74 mmol/L and < 7.74 mmol/L at baseline	≥ 6.20 mmol/L and < 6.20 mmol/L at baseline	≥7.74 [≥6.20] mmol/L and < 7.74 [<6.20] mmol/L at baseline
Triglycerides	≥4.6 mmol/L and < 4.6 mmol/L at baseline	Fasted level ≥5.64 mmol/L and < 5.64 mmol/L at baseline	≥4.6 [≥5.64 fasted] mmol/L and < 4.6 [<5.64 fasted] mmol/L at baseline

Parameter	Adults (≥18) a	Adolescents (≥12 to <18) a	Combined
Glucose Hypoglycaemia Hyperglycaemia	(≤3.9 mmol/L and <LLN) and (>3.9 mmol/L or ≥LLN) at baseline  ≥11.1 mmol/L (unfasted) and <11.1 mmol/L (unfasted) at baseline; ≥7 mmol/L (fasted) and <7 mmol/L (fasted) at baseline	<2.7 mmol/L and ≥2.7 mmol/L at baseline (or < 50 mg/dL and ≥ 50 mg/dL at baseline)  ≥10 mmol/L (unfasted) and < 10 mmol/L (unfasted) at baseline (or ≥180 mg/dl and <180 mg/dl at baseline); ; ≥7 mmol/L (fasted) and <7 mmol/L (fasted) at baseline (or ≥120 mg/dL and <120 mg/dL at baseline)	(≤3.9 [ $<2.7$ ] mmol/L and <LLN) and (>3.9 [ $\geq 2.7$ ] mmol/L or ≥LLN) at baseline  ≥11.1 [ $\geq 10$ ] mmol/L (unfasted) and <11.1 [ $<10$ ] mmol/L (unfasted) at baseline; ≥7 mmol/L (fasted) and <7 mmol/L (fasted) at baseline
HbA1c b	>8% and ≤ 8% at baseline	>6.5% and ≤ 6.5% at baseline	>8% [ $>6.5\%$ ] and ≤ 8% [ $\leq 6.5\%$ ] at baseline
Albumin	≤25 g/L and >25 g/L at baseline	≤25 g/L and >25 g/L at baseline	≤25 g/L and >25 g/L at baseline
CRP b	>2 ULN or >10 mg/L (if ULN not provided) and ≤2 ULN or ≤10 mg/L (if ULN not provided) at baseline	NONE	>2 ULN or >10 mg/L (if ULN not provided) and ≤2 ULN or ≤10 mg/L (if ULN not provided) at baseline (adults only)
Calcium total	NONE	<2 mmol/L and baseline ≥2 mmol/L (or ≤ 8 mg/dL and baseline >8 mg/dL)  ≥2.9 mmol/L and baseline <2.9 mmol/L (or ≥11.6 mg/dL and baseline <11.6 mg/dL)	<2 mmol/L and baseline ≥2 mmol/L (adolescents only)  ≥2.9 mmol/L and baseline <2.9 mmol/L (adolescents only)
LDL Cholesterol	NONE	≥4.91 mmol/L and <4.91 mmol/L at baseline (≥ 190 mg/dl and <190 mg/dl at baseline)	≥4.91 mmol/L and <4.91 mmol/L at baseline (adolescents only)
Hematology			
WBC	<3.0 Giga/L and ≥3.0 Giga/L at baseline (Non-Black);  <2.0 Giga/L and ≥2.0 Giga/L at baseline (Black)  ≥16.0 Giga/L and < 16 Giga/L at baseline	<4.0 Giga/L and ≥4.0 Giga/L at baseline  >13.5 Giga/L and ≤13.5 Giga/L at baseline	<3.0 Giga/L and ≥3.0 Giga/L at baseline (Non-Black); <2.0 Giga/L and ≥2.0 Giga/L at baseline (Black) [ $<4.0$ Giga/L and ≥4.0 Giga/L at baseline]  ≥16.0 [ $>13.5$ ] Giga/L and < 16 [ $\leq 13.5$ ] Giga/L at baseline
Lymphocytes	>4.0 Giga/L and ≤ 4.0 Giga/L at baseline	<0.6 Giga/L and ≥0.6 Giga/L at baseline  >6.0 Giga/L and ≤6.0 Giga/L at baseline	<0.6 Giga/L and ≥0.6 Giga/L at baseline (adolescents only)  >4.0 [ $>6.0$ ] Giga/L and ≤4.0 [ $\leq 6.0$ ] Giga/L at baseline

Parameter	Adults (≥18) a	Adolescents (≥12 to <18) a	Combined
Neutrophils	<1.5 Giga/L and ≥1.5 Giga/L at baseline (Non-Black); <1.0 Giga/L and ≥1.0 Giga/L at baseline (Black)	<1.2 Giga/L and ≥1.2 Giga/L at baseline >ULN and baseline ≤ ULN	<1.5 Giga/L and ≥1.5 Giga/L at baseline (Non-Black); <1.0 Giga/L and ≥1.0 Giga/L at baseline (Black) [ <1.2 Giga/L and ≥1.2 Giga/L at baseline]  >ULN and baseline ≤ ULN (adolescents only)
Monocytes	>0.7 Giga/L ≤ 0.7 Giga/L at baseline	>1.2 Giga/L and ≤ 1.2 Giga/L at baseline	>0.7 [1.2] Giga/L ≤ 0.7 [1.2] Giga/L at baseline
Basophils	>0.1 Giga/L ≤ 0.1 Giga/L at baseline	NONE	>0.1 Giga/L ≤ 0.1 Giga/L at baseline (adults only)
Eosinophils	(>0.5 Giga/L and >ULN) and (≤0.5 Giga/L or ≤ ULN at baseline)	(>0.5 Giga/L and >ULN) and (≤0.5 Giga/L or ≤ ULN at baseline)	(>0.5 Giga/L and >ULN) and (≤0.5 Giga/L or ≤ ULN at baseline)
Hemoglobin	≤115 g/L and > 115 g/L at baseline for male; ≤95 g/L and > 95 g/L at baseline for Female.  ≥185 g/L and <185 g/L at baseline for Male; ≥165 g/L and < 165 g/L at baseline for Female  Decrease from Baseline ≥20 g/L	<100 g/L and ≥100 g/L at baseline  ≥200 g/L and <200 g/L at baseline	≤115 g/L and > 115 g/L at baseline for male; ≤95 g/L and > 95 g/L at baseline for Female. [ <100 g/L and ≥100 g/L at baseline]  ≥185 g/L and <185 g/L at baseline for Male; ≥165 g/L and < 165 g/L at baseline for Female [≥200 g/L and <200 g/L at baseline]  Decrease from Baseline ≥20 g/L
Hematocrit	≤0.37 v/v and > 0.37 v/v at baseline for Male ; ≤0.32 v/v and > 0.32 v/v at baseline for Female  ≥0.55 v/v and < 0.55 v/v at baseline for Male ; ≥0.5 v/v and < 0.5 v/v at baseline for Female	≤0.37 v/v and >0.37 v/v at baseline for Male; ≤0.33 v/v and >0.33 v/v at baseline for Female  ≥0.52 v/v and <0.52 v/v at baseline for Male; ≥0.47 v/v and <0.47 v/v at baseline for Female	≤0.37 v/v and > 0.37 v/v at baseline for Male ; ≤0.32 [≤0.33] v/v and > 0.32 [≥0.33] v/v at baseline for Female  ≥0.55 [≥0.52] v/v and < 0.55 [≤0.52] v/v at baseline for Male ; ≥0.5 [≥0.47] v/v and < 0.5 [≤0.47] v/v at baseline for Female

Parameter	Adults (≥18) a	Adolescents (≥12 to <18) a	Combined
RBC	<4 Tera/L and baseline ≥4 Tera/L For Male; <3 Tera/L and baseline ≥3 Tera/L for Female  ≥7 Tera/L and baseline < 7 Tera/L for Male; ≥6 Tera/L and baseline < 6 Tera/L for Female	NONE	<4 Tera/L and baseline ≥4 Tera/L For Male; <3 Tera/L and baseline ≥3 Tera/L for Female  ≥7 Tera/L and baseline < 7 Tera/L for Male; ≥6 Tera/L and baseline < 6 Tera/L for Female
Platelets	<100 Giga/L and ≥100 Giga/L at baseline  ≥700 Giga/L and < 700 Giga/L at baseline	<100 Giga/L and ≥100 Giga/L at baseline  >700 Giga/L and ≤ 700 Giga/L at baseline	<100 Giga/L and ≥100 Giga/L at baseline  ≥700 Giga/L and < 700 Giga/L at baseline
Urinalysis			
pH	≤4.6 and > 4.6 at baseline ≥8 and < 8 at baseline	NONE	≤4.6 and > 4.6 at baseline (adults only) ≥8 and < 8 at baseline (adults only)
Ketonuria	NONE	Presence and absence at baseline	Presence and absence at baseline (adolescents only)
Glycosuria	NONE	Presence and absence at baseline	Presence and absence at baseline (adolescents only)
Microscopic Hematuria	NONE	> 5 RBCs/ HPF and ≤5 RBCs/ HPF at baseline	> 5 RBCs/ HPF and ≤5 RBCs/ HPF at baseline (adolescents only)
Proteinuria	NONE	≥ 1+ and <1 at baseline	≥ 1+ and <1 at baseline (adolescents only)
Vital signs			
HR	≤50 bpm and decrease from baseline ≥20 bpm ≥120 bpm and increase from baseline ≥20 bpm	≤50 bpm and decrease from baseline ≥20 bpm ≥120 bpm and increase from baseline ≥20 bpm	≤50 bpm and decrease from baseline ≥20 bpm ≥120 bpm and increase from baseline ≥20 bpm
SBP	≤95 mmHg and decrease from baseline ≥20mmHg ≥160 mmHg and increase from baseline ≥20 mmHg	≤90 mmHg and decrease from baseline ≥20 mmHg ≥119 mmHg and increase from baseline ≥20 mmHg	≤95 mmHg [≤90 mmHg] and decrease from baseline ≥20mmHg  ≥160 mmHg [≥119 mmHg] and increase from baseline ≥20 mmHg

Parameter	Adults (≥18) a	Adolescents (≥12 to <18) a	Combined
DBP	≤45 mmHg and decrease from baseline ≥10 mmHg ≥110 mmHg and increase from baseline ≥10 mmHg	≤54 mmHg and decrease from baseline ≥10 mmHg ≥78 mmHg and increase from baseline ≥10 mmHg	≤45 mmHg [≤54 mmHg] and decrease from baseline ≥10 mmHg ≥110 mmHg [≥78 mmHg] and increase from baseline ≥10 mmHg
Temperature	Rectal, ear: >100.4 °F/38.0 °C Oral: >99.5 °F/37.5 °C Axillary or skin infrared (temporal): >99 °F/37.2 °C	Rectal, ear: >100.4 °F/38.0 °C Oral: >99.5 °F/37.5 °C Axillary or skin infrared (temporal): >99 °F/37.2 °C	Rectal, ear: >100.4 °F/38.0 °C Oral: >99.5 °F/37.5 °C Axillary or skin infrared: >99 °F/37.2 °C
Respiratory rate	<12 per minute and ≥12 per minute at baseline  >20 per minute and ≤20 per minute at baseline	<12 per minute and ≥12 per minute at baseline  >20 per minute and ≤20 per minute at baseline	<12 per minute and ≥12 per minute at baseline  >20 per minute and ≤20 per minute at baseline
Weight	≥5% increase from baseline ≥5% decrease from baseline	≥5% weight loss from baseline	≥5% increase from baseline (adults only) ≥5% decrease from baseline
ECG			Ref.: CPMP 1997 guideline.
HR	≤50 bpm and decrease from baseline ≥20 bpm ≥120 bpm and increase from baseline ≥20 bpm	≤50 bpm and decrease from baseline ≥20 bpm ≥120 bpm and increase from baseline ≥20 bpm	≤50 bpm and decrease from baseline ≥20 bpm ≥120 bpm and increase from baseline ≥20 bpm
PR	≥220 ms and increase from baseline ≥20 ms	≥200 ms and < 200 ms at baseline	≥220 ms and increase from baseline ≥20 ms [≥200 ms and < 200 ms at baseline]
QRS	≥120 ms & < 120 ms at baseline	≥110 ms & < 110 ms at baseline	≥120 [≥110] ms and < 120 [<110] ms at baseline

Parameter	Adults (≥18) a	Adolescents (≥12 to <18) a	Combined
QTc	Absolute values (ms)	Absolute values (ms)	Absolute values (ms)
Borderline	Borderline:	Borderline:	Borderline:
Prolonged	431-450 ms and < 431ms at baseline for Male;	431-450 ms and < 431ms at baseline for Male;	431-450 ms and < 431ms at baseline for Male;
Additional	451-470 ms and < 451 ms at baseline for Female	451-470 ms and < 451 ms at baseline for Female	451-470 ms and < 451 ms at baseline for Female
	Prolonged:	Prolonged:	Prolonged:
	>450 to <500 ms and ≤ 450 ms at baseline for Male;	>450 to <500 ms and ≤ 450 ms at baseline for Male;	>450 to <500 ms and ≤ 450 ms at baseline for Male;
	>470 to <500 ms and ≤ 470 ms at baseline for Female	>470 to <500 ms and ≤ 470 ms at baseline for Female	>470 to <500 ms and ≤ 470 ms at baseline for Female
	Additional:	Additional:	Additional:
	≥500 ms and < 500 ms at baseline	≥500 ms and < 500 ms at baseline	≥500 ms and < 500 ms at baseline
	Increase from baseline	Increase from baseline	Increase from baseline
	Borderline: Increase from baseline 30-60 ms	Borderline: Increase from baseline 30-60 ms	Borderline: Increase from baseline 30-60 ms
	Prolonged: Increase from baseline >60 ms	Prolonged: Increase from baseline >60 ms	Prolonged: Increase from baseline >60 ms

a The ULN is based upon central lab reference ranges. The reference range might be different for different age-groups. For the purpose of this study in a particular patient the reference range based upon age at baseline will be used as reference throughout the study for determining PCSVs.

b Lab parameters not collected in this study.

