6.2. Study Population

Eligible patients for this study consist of adult males and females ≥ 18 years of age and adolescent males and females ≥ 12 to < 18 years of age at the time of study entry with EoE. At least 10% of patients enrolled in Part B will be adolescents ≥ 12 to < 18 years of age. At least 30% of patients enrolled in Part B must have a history of prior use of swallowed topical corticosteroids for the treatment of EoE.

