#### 3.2. The Safety Analysis Set (SAF)

##### Part B:

The Part B safety analysis set (SAF) includes all randomized patients who received any study drug in Part B; it is based on the treatment received (as treated). Treatment compliance/administration and all clinical safety variables in Part B will be analyzed using the Part B SAF.

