### 5.7.2. Clinical Laboratory Measurements

Laboratory measurements include clinical chemistry, hematology and urinalysis results, and will be converted to values in standard international units. Summaries of laboratory variables will include:

- Descriptive statistics of laboratory result and change from baseline by visit.
- The number (n) and percentage (%) of subjects with treatment-emergent PCSVs. This summary will be provided based on all patients in the SAF as well as in the subgroup of SAF patients who did not meet the PCSV criterion at baseline.
- Shift tables based on baseline normal/abnormal and other tabular and graphical methods may be used to present the results for parameters of interest

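### As worded, the SAP divides laboratory PCSV rows that apply to one age group by all safety-set patients, understating adolescent-only percentages up to 10-fold at the 10% enrolment minimum

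*SAP*

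**What the plan says.** SAP 5.7.2 plans the number and percentage of subjects with treatment-emergent laboratory PCSVs. It gives the basis: "This summary will be provided based on all patients in the SAF", and then "as well as in the subgroup of SAF patients who did not meet the PCSV criterion at baseline". SAP 3.2 defines the Part B SAF without an age split; it "includes all randomized patients who received any study drug in Part B".

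SAP 11.3 has an adult, an adolescent and a Combined set of criteria, and says that the Combined "column will be used for display in the reporting outputs". The laboratory rows with a criterion for one age group only include:

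- **Adolescents only:** low calcium ("<2 mmol/L and baseline ≥2 mmol/L (adolescents only") and high calcium, LDL cholesterol ("≥4.91 mmol/L and <4.91 mmol/L at baseline (adolescents only"), lymphocytes below 0.6 Giga/L, neutrophils above ULN, ketonuria, glycosuria (both "Presence and absence at baseline (adolescents only"), microscopic hematuria and proteinuria.
- **Adults only:** basophils, urine pH, RBC, and a hemoglobin decrease of at least 20 g/L. The last two carry no adults-only label in the Combined column, although RBC shows NONE for adolescents and the hemoglobin decrease appears only in the adult column.

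Among the vital signs, weight gain of at least 5% is marked adults only. SAP 5.7.3, which covers vital signs, names no denominator.

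On the age mix, Protocol 6.2 gives only a floor: "At least 10% of patients enrolled in Part B will be adolescents". Neither document gives the actual share.

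**The concern.** The adolescent-specific criteria exist so that laboratory abnormalities in patients aged 12 to under 18 can be reported. If the percentage is taken over a population made up mostly of adults, for whom the criterion is undefined, the printed figure is not an incidence in any group to which the criterion applies. It also cannot be compared with neighbouring rows that apply to everyone.

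Safety in adult and adolescent patients is a secondary objective (Protocol 2.2, SAP 1.2.2), so these tables are a natural place to look for adolescent incidence. The baseline-restricted summary does not solve the problem: an adult cannot have met an adolescent-only criterion at baseline and so, read literally, stays in.

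Nothing else in the plan reliably supplies the right percentage. SAP 3.5 lists age group for safety subgroup analyses, but allows a subgroup to be skipped when it is small, with under 20 patients per arm as the example. SAP 11.1.3 enters No under subgroup analysis for laboratory measures.

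**Working it through.** The plan states no percentage or dilution factor for these rows, so there is no figure to reproduce.

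**Inputs**

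- Arm size: 70 per group, 3 × 70 = 210 (SAP 2.1, Protocol 6.1). The arithmetic treats all of them as treated.
- Adolescent share s: at least 10% of Part B (Protocol 6.2). Higher values are assumptions.
- Randomization stratified by age (SAP 2.1), so s is taken as about equal across arms.
- Denominator: all SAF patients in the arm (SAP 5.7.2).

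**Formulas**

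With x adolescent cases in an arm of 70, the printed rate is x/70 and the rate among patients who can meet the criterion is x/(70s). The understatement factor is (x/70s) ÷ (x/70) = 1/s. For an adult-only row it is 1/(1 − s). The largest percentage an adolescent-only row can print is s itself.

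| Share s | Adolescents per arm | One case: applicable rate | One case: printed | Factor, adolescent-only | Factor, adult-only |
|---|---|---|---|---|---|
| 10% (minimum) | 7 | 14.3% | 1.4% | 10.0 | 1.11 |
| 20% (assumed) | 14 | 7.1% | 1.4% | 5.0 | 1.25 |
| 28.6% (assumed) | 20 | 5.0% | 1.4% | 3.5 | 1.40 |
| 33% (assumed) | 23.1 | 4.3% | 1.4% | 3.0 | 1.49 |

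At the minimum share, an abnormality in all seven adolescents of an arm would print as 7/70 = 10%.

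**Risk difference.** Suppose 3 of 7 adolescents on one arm and 0 of 7 on the other. The difference is 3/7 = 42.9 percentage points; over 70 per arm it prints as 3/70 = 4.3 points, again a factor of 10.

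**Relative comparison.** With equal shares, the ratio of two arms is (x₁/70) ÷ (x₂/70) = x₁/x₂ under either denominator, so it does not change.

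**Second summary.** Of the patients assigned to these rows, only adolescents can be removed for meeting the criterion at baseline. If k are removed, the factor is (70 − k)/(70s − k), which is no smaller than 1/s. The restriction therefore does not reduce the dilution.

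**Link to the subgroup clause.** Twenty adolescents per arm is 20/70 = 28.6%, a factor of 3.5. If the example threshold in SAP 3.5 is applied, every share at which the age subgroup may be skipped has a factor above 3.5.

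**The case against.** The strongest reply is that the SAP does not explicitly say how an age-restricted row is divided. SAP 5.7.2 names populations for the summary as a whole, SAP 11.3 says that applicable criteria will be applied, and most of these rows are labelled. A programmer could treat adults as not evaluable, and the table shells are not in the documents. This stands as a limit: the point rests on the plain wording, not on a table that has been seen. It does not remove the point. The only denominator wording for laboratory PCSVs is all SAF patients, and two adult-only criteria have no label to guide anyone.

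The subgroup argument should not be pressed too hard. The small-subgroup clause in SAP 3.5 is permissive. SAP 11.1.3 also enters No for adverse events, although SAP 5.7.1 plans adverse event tables for selected subgroups, so that table is not a firm override. Out-of-range laboratory values are flagged in listings (Protocol 10.4.4.2), and abnormal results with symptoms or needing intervention are reportable as adverse events (Protocol 9.4.5). These are other routes to an adolescent signal, but none gives an incidence.

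A reader might infer more than the documents support:

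- **That a real adolescent signal would be hidden.** The count is right and a labelled 3 versus 0 would be visible. In that example the two-sided Fisher p-value is 0.19 for 3/7 v 0/7 and 0.24 for 3/70 v 0/70, so the evidence hardly changes. No formal test of PCSVs between arms is planned.
- **That the factor is 10.** That is its value at an enrolment minimum, and it falls as the share rises.
- **That rows with two thresholds (systolic and diastolic pressure, BUN) have the same error.** They do not. Every patient is evaluable against a cut-off for his or her age, so nothing is diluted; splitting them by age is a matter of preference.
- **That vital signs are expressly divided by all SAF patients.** SAP 5.7.3 is silent on this.

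**Conclusion.** The point holds for laboratory PCSV rows defined for one age group only. Followed as written, SAP 5.7.2 with the Combined column of SAP 11.3 keeps patients who cannot meet the criterion in the denominator. In the all-SAF summary, adolescent-only percentages and risk differences are understated by one over the adolescent share: up to 10-fold at the 10% minimum, 5-fold at an assumed 20%, about 3-fold at an assumed 33%. Adult-only rows are affected little (1.11-fold at a 10% adolescent share). Counts are correct, and comparisons in relative terms are largely unaffected.

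This rests on three assumptions: that all SAF patients means what it says for every row, that arms are close to 70, and that age stratification keeps the adolescent share similar across arms. A single arm, or the Part C SAF, could differ somewhat. The plan should be corrected because a stated rule gives a wrong percentage and is cheap to repair; it does not put the treatment comparison in doubt.

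**What to change.** In SAP 5.7.2 and 11.3, state the following:

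- For any PCSV criterion defined for only one age group, whether or not the Combined column labels it so, the denominator is the SAF patients in that age group with at least one post-baseline assessment of the parameter, shown as n/N1 (%).
- For microscopic hematuria, the denominator is SAF adolescents with at least one post-baseline urinalysis, and a normal dipstick counts as not meeting the criterion. Microscopy is done only after an abnormal dipstick (SAP 4.5.2), so requiring a microscopy value would select patients with abnormal urine and inflate the rate.
- The restriction to patients not meeting the criterion at baseline applies to the second summary only. A baseline value should not be required in the first, because SAP 6.3 counts a post-baseline PCSV with a missing baseline as treatment-emergent; such a patient would otherwise be in the numerator but not the denominator.

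Apply the same denominator to the adults-only weight-gain row in SAP 5.7.3, and add the adults-only label to the RBC and hemoglobin-decrease rows. Tabulating two-threshold rows by age is optional.

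The cost is a short SAP rule and revised table shells, with no new data. The downside is small adolescent denominators, about 7 per arm at the minimum share, where one case moves the percentage by 14 points; showing n/N1 makes this plain.

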##### Blood Chemistry

Sodium	Total protein, serum	Total and indirect bilirubin
Potassium	Creatinine	Total cholesterol
Chloride	Blood urea nitrogen (BUN)	Low-density lipoprotein (LDL)
Carbon dioxide	AST	High-density lipoprotein (HDL)
Calcium	ALT	Triglycerides
Glucose	Alkaline phosphatase	Uric acid
Albumin	Lactate dehydrogenase (LDH)	Creatine phosphokinase (CPK) 

 CPK isoenzymes will be measured when CPK >5 × ULN

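### SAP 11.3 leaves its conjugated-bilirubin PCSV row unreported, although direct bilirubin can be derived from the total and indirect results already collected

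*SAP*

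**What the plan says.** SAP 11.3 has a full row for conjugated bilirubin. The adult condition is "Direct Bilirubin >35% Total Bilirubin and Total Bilirubin >1.5 ULN" and the adolescent condition is "Direct Bilirubin >35% Total Bilirubin and Total Bilirubin ≥1.3 ULN". In each case the pair of conditions must not both have been met at baseline. The row carries footnote b, which reads "Lab parameters not collected in this study"; HbA1c and CRP carry it too. The introduction to the section sets the scope: "Applicable criteria will be applied to parameters collected in the study to identify treatment-emergent PCSV cases". Together these mean the row will not appear in the safety tables.

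The blood chemistry panels in Protocol 8.2.3.5 and SAP 4.5.2 each list "Total and indirect bilirubin". Neither lists direct bilirubin, and neither document says that it will be derived.

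The rows for ALT, AST, alkaline phosphatase, total bilirubin, and ALT or AST combined with total bilirubin carry no footnote b and will be reported. The adult total-bilirubin row is ">1.5 and ≤ 2 ULN and baseline ≤ 1.5 ULN >2 ULN and baseline ≤ 2.0 ULN"; the adolescent one is "≥1.3 ULN and baseline < 1.3 ULN".

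**The concern.** Footnote b fits HbA1c and CRP: neither is in the panel and neither can be worked out from it. Conjugated bilirubin is different, because both quantities needed to compute it are measured at every chemistry draw. The SAP has specified a criterion, has the data to run it, and leaves it out.

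The direct share matters for reading a bilirubin signal. It separates a mainly indirect rise from a mainly direct one, and Protocol 7.4.2.1 recognises that kind of distinction when it sets confirmed Gilbert's Syndrome apart. No other PCSV row uses the direct share. Protocol 10.4.4.2 promises a PCSV count for each laboratory test, with the criteria left to the SAP.

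**Working it through.** There is no figure in the plan to reproduce, so the check is whether the row can be computed and what it would add to the rows that are kept. Write T for total, I for indirect and D for direct bilirubin, all in multiples of the ULN for total bilirubin.

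**1. Can the row be computed?** D = T − I, so D/T > 35% is the same test as I/T < 65%. With T = 2.0 and I = 1.2, D = 2.0 − 1.2 = 0.8 and D/T = 0.8/2.0 = 40%, which is above 35%. Both inputs are in the panel.

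**2. What classification is lost?** Take two adults, both at T = 2.2 after a baseline total of 2.0 or less.
- I = 1.98: D/T = (2.2 − 1.98)/2.2 = 10%, criterion not met.
- I = 0.88: D/T = (2.2 − 0.88)/2.2 = 60%, criterion met (provided it was not already met at baseline).

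The total-bilirubin row counts both in its >2 ULN tier and does not distinguish them.

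**3. Which patients are still flagged on total bilirubin?** The unreported row itself requires a post-baseline total above 1.5 in adults.
- Adult baseline ≤ 1.5: a later total above 1.5 and up to 2 meets the first tier, and a later total above 2 meets the second. Every such patient is flagged.
- Adult baseline above 1.5 and up to 2: flagged only if the later total exceeds 2.
- Adult baseline above 2: never flagged by this row.
- Adolescent baseline < 1.3: a later total ≥ 1.3 is always flagged. From a baseline ≥ 1.3 the adolescent column flags nothing. If the >2 ULN tier in the Combined column is also applied to adolescents, a rise from ≤ 2 to above 2 would be caught as well.

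This was checked by enumeration, with T from 0.2 to 5.0 in steps of 0.1 and D/T from 0 to 100% in steps of 5 points, at baseline and post-baseline. No case meeting the conjugated-bilirubin criterion but missed by the total-bilirubin row had a baseline total ≤ 1.5 (adults) or < 1.3 (adolescents). All missed cases had a baseline direct share of 35% or less.

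**4. An example of a missed flag.** An adult has baseline T = 2.1 with 10% direct (D = 0.21) and later T = 2.5 with 50% direct (D = 1.25).
- Total-bilirubin row: 2.5 is above 2, but the baseline of 2.1 exceeds 2.0, so there is no flag.
- Combined row: no flag unless ALT or AST exceeds 3 ULN.
- Conjugated-bilirubin row: 50% > 35%, 2.5 > 1.5, and the baseline share of 10% is ≤ 35%, so it would flag.

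**5. Can such a patient be in the trial?** The hepatic exclusion in Protocol 6.2.2 rests on current treatment for liver disease or persistently raised transaminases, and the listed laboratory exclusions are platelets, neutrophils and eGFR. No bilirubin limit is stated, although the investigator-judgement exclusions could keep some such patients out.

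**The case against.** The strongest reply is that the documents agree with each other. Direct bilirubin is not a listed test, footnote b says only that the parameter is not collected, and the scope sentence limits the table to collected parameters. Derivable is not the same as collected. This stands: a reader might infer that the footnote contradicts the panel, and it does not.

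A reader might also infer that the trial loses its detection of liver injury. The documents do not support that either. The remaining liver rows are intact, and step 3 shows that patients without a raised baseline total are still flagged.

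Nor is the underlying information gone. SAP 5.7.2 summarises laboratory results by visit, and Protocol 10.4.4.2 provides listings that flag out-of-range values, so total and indirect results can be compared patient by patient. With few cases that is feasible.

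Finally, the combined row's reliance on total bilirubin does not come from footnote b and would not change with the fix. Its thresholds match those in Protocol 7.4.2.1.

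These replies shrink the point but leave two things unanswered: the PCSV table will not separate direct from indirect rises, and the patient in step 4 appears in no bilirubin PCSV row.

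**Conclusion.** This is a minor gap in descriptive safety reporting, and closing it is a free improvement. The loss is the direct/indirect split among patients flagged on total bilirubin, and the flag itself in patients who start with a raised, mainly indirect total and shift to a direct share above 35%.

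The documents give no rate of raised bilirubin, so the number affected cannot be stated; it is probably small. For scale only, one patient is 1/70 = 1.4% of a planned Part B arm. The values in steps 1, 2 and 4 are illustrations, not data. No endpoint, alpha level or power figure changes.

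The conclusion assumes that total and indirect bilirubin are reported from the same sample in the same units. The documents do not say how the central laboratory obtains the indirect value.

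**What to change.** In SAP 11.3, remove footnote b from the conjugated-bilirubin row and keep it for HbA1c and CRP. Add one line: *Direct bilirubin = total bilirubin − indirect bilirubin from the same sample, where both are reported.* Apply the criterion as already written and show it beside the other liver PCSV rows.

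The cost is one footnote edit and one derived variable, with no new sample or test. If the sponsor prefers not to derive direct bilirubin, deleting the row and stating that the direct share will not be assessed would at least make the omission explicit.
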